7.3.2. Study items

Enter the following information in CRF.

7.3.2.1. Information to identify the subject

(1) ID number

(2) Gender

(3) Date of birth (age at the start of treatment with this drug at the site if the information cannot be disclosed)

For sites participating in THAOS within the observation period, the following information should also be entered:

- (1) THAOS registration status
- (2) THAOS case number

7.3.2.2. State of concurrent medical examination

Regarding the status of concurrent medical examination after the start of treatment with this drug until the end of observation period, enter the following information:

(1) Prescription of this drug or treatment of the target disease at sites other than this hospital

(2) If Yes for concurrent medical examination, name of site

7.3.2.3. Patient characteristics

Enter the following information at the start of treatment with this drug.

(1) Experience of treatment with this drug

(2) Classification of inpatient/outpatient

(3) Target disease and onset timing

(4) Diagnosis of TTR amyloidosis

(Mutant genotype and timing of identification, diagnostic method [including the conduct of tissue biopsy], Karnofsky index*)

(5) Family history of TTR-FAP

(6) Classification of accumulated cases/non-accumulated cases

Enter the classification of accumulated/non-accumulated area as the patient's birthplace.

In this study, Nagano, Kumamoto, and Ishikawa prefectures are defined as accumulated areas.

(7) History of organ transplant (timing of transplant, name of transplanted organ [including the presence or absence of liver transplant and its timing])

(8) Presence/absence and severity of hepatic/renal impairment

If "Yes" for hepatic impairment, enter the reason for judgment of severity.

(9) Medical history (past history/complications)

Table 2.Karnofsky index

*Karnofsky index (Karnofsky Performance Status) $(\%)^{(2)-8)}$

- 100 : Normal; no complaints; no evidence of disease.
- 90 : Able to carry on normal activity; minor signs or symptoms of disease.
- 80 : Normal activity with effort; some signs or symptoms of disease.
- 70 : Cares for self; unable to carry on normal activity or to do active work.
- 60 : Requires occasional assistance, but is able to care for most of their personal needs.
- 50 : Requires considerable assistance and frequent medical care.
- 40 : Disabled; requires special care and assistance.
- 30 : Severely disabled; hospital admission is indicated although death not imminent.
- 20 : Very sick; hospital admission is necessary although death not imminent.
- 10 : Moribund; fatal processes progressing rapidly.
- 0 : Dead

7.3.2.4. Previous treatment drugs

Enter all drugs used for the treatment of the target disease from 24 weeks before the start of treatment with this drug until the day before the first day of treatment (including NSAIDs).

(1) Drug name, dosage form

(2) Dose and frequency of daily dose

- (3) Duration of treatment
- (4) Reason for discontinuation

7.3.2.5. Pregnancy

If the patient is female, enter the presence or absence of pregnancy (if she is pregnant, date of delivery or expected date of delivery) from the first day of treatment with this drug until the end of observation period (or date of discontinuation of treatment with this drug) in each booklet.

7.3.2.6. Targeted drug use record

Enter the following information on the status of using this drug from the first day of treatment with this drug until the end of observation period (or date of discontinuation of treatment with this drug).

- (1) Dose
- (2) Frequency of daily dose
- (3) Duration of treatment
- (4) Reason for change/washout

7.3.2.7. Concomitant therapy

7.3.2.7.1. Drug therapy

For all drugs used from the first day of treatment with this drug until the end of the observation period (or date of discontinuation of treatment with this drug), enter the information on administration (e.g., name of drug [product name], route of administration, dose, duration of treatment, and presence or absence of any action taken for adverse events). Also, enter drugs administered for the treatment of adverse events.

7.3.2.7.2. Non-drug therapy

For all non-drug therapies provided from the first day of treatment with this drug until the end of the observation period (or date of discontinuation of treatment with this drug), enter the name of therapy, implementation period, and presence or absence of any action taken for adverse events. Also, enter therapies provided for the treatment of adverse events.

7.3.2.8. Tests/clinical laboratory tests

For the following test items conducted from the first day of treatment with this drug until the end of the observation period (or date of discontinuation of treatment with this drug), enter the test dates (dates of measurement) and test results. For the tests conducted before the start of treatment with this drug, enter the test results immediately before the first day of treatment (including the first day of treatment). For clinically significant fluctuations compared to those before the start of treatment with this drug, enter the details in the adverse event column.

7.3.2.8.1. Clinical laboratory tests

(1) Hematology: White blood cell count, neutrophil count, lymphocyte count, red blood cell count, platelet count, hemoglobin, prothrombin time

(2) Biochemistry: AST (GOT), ALT (GPT), AL-P, LDH, γ -GTP, total bilirubin, triglycerides, serum creatinine, serum albumin

(3) Endocrine test: Thyroid-stimulating hormone (TSH), total T4, free thyroxine (FT4)

(4) Urinalysis: Urine protein (qualitative)

Pfizer Confidential Page 17 of 37

7.3.2.8.2. General tests

- (1) Height
- (2) Weight
- (3) Pulse
- (4) Blood pressure (systolic/diastolic)

7.3.2.8.3. Plasma concentration of tafamidis (to be performed only for patients with severe hepatic impairment)

If the patient has severe hepatic impairment, measure the plasma concentration of tafamidis as much as possible and enter the following information. If the patient has hepatic function disorder at the start of treatment with this product, enter the details in the section of "Presence or absence of hepatic/renal impairment" and if it occurred during the observation period, enter the details in the section of "Adverse Events". If a laboratory test related to hepatic impairment is performed, enter the test results in the section of "Laboratory tests" or the section of "Tests for adverse events".

For the detailed method of measuring plasma concentration of tafamidis, refer to the Appendix to Guidelines for Special Investigation "Procedures for Measurement Plasma Concentration of Tafamidis in Patients with Severe Hepatic Impairment" (Appendix 1).

- (1) Record of medicines immediately before blood sampling (date and time of medicines)
- (2) Record of blood sampling (date and time of blood sampling)
- (3) Plasma concentration of tafamidis

Table 3. Child-Pugh Classification

*Overseas clinical studies were conducted by defining moderate hepatic impairment as Child-Pugh score of ≤ 9 . [Reference: Child-Pugh classification] The scores for each item are totaled and 5 to 6 points are classified as A, 7 to 9 points as B, and 10 to 15 points as C.

[Child-Pugh classification]	1 point	2 points	3 points
Hepatic encephalopathy	None	Mild	Occasional coma
Ascites	None	Small amount	Moderate amount
Total serum bilirubin (mg/dL)	<2.0	2.0-3.0	3.0<
Serum albumin (g/dL)	3.5<	2.8-3.5	<2.8
Prothrombin time (%)	70<	40-70	<40

7.3.2.8.4. Cardiovascular assessment

- (1) Standard 12-lead ECG
- (2) Echocardiography

7.3.2.8.5. Assessment of neurological function (NIS)

Enter scores for the following (1) to (4) items according to the assessment indicators for neurological function shown below by using Neuropathy Impairment Score $(NIS)^{9}$.

[Timing of assessment] Before the start of treatment (results immediately before treatment including the first day of treatment), Week 78 (1.5 years later), Week 156 (3 years later) (or at discontinuation of treatment with this drug)

(1) Cranial Nerves: Items 1 to 5(2) Muscle Weakness: Items 6 to 24

Cranial nerves and muscle weakness will be graded on the following 8-point scale: 0 = Normal 1 = 25% Weak 2 = 50% Weak 3 = 75% Weak 3.25 = Move against gravity 3.5 = Movement, gravity eliminated 3.75 = Muscle flicker, no movement 4 = Paralysis

(3) Reflexes: Items 25 to 29(4) Sensation: Index finger (items 30 to 33), great toe (items 34 to 37)

Tendon reflexes (reflexes) and sensation of index and great toes (sensation; tactile sense, pain sensation, vibration sense, joint sense) will be graded on the following 3-point scale: 0 = Normal

1 = Decreased

2 = Absent

7.3.2.8.6. Quality of life (QOL)

The QOL will be assessed using Norfolk Quality of Life-Diabetic Neuropathy (Norfolk QOL-DN)^{10), 11)}. Norfolk QOL-DN is a self-completed assessment scale for patients with neuropathy that can quantify the impact of neuropathy on QOL. This scale consists of 35 questions, each of which relates to the following functions and symptoms:

TQOL score, physical function/large nerve fiber disorder score, activities of daily living score, symptom score, small nerve fiber disorder score, autonomic neuropathy score

For data collection, the Norfolk QOL-DN questionnaire (Appendix 2) will be used to answer all questions by the patient himself or herself as much as possible. The investigator will complete the study items by referring to the questionnaires.

[Timing of assessment] Before the start of treatment (results immediately before treatment including the first day of treatment), Week 78 (1.5 years later), Week 156 (3 years later) (or at discontinuation of treatment with this drug)

7.3.2.8.7. Ambulatory status

Ambulatory status will be assessed using the ambulatory ability scale in the polyneuropathy dysfunction score.

Pfizer Confidential Page 19 of 37 [Timing of assessment] Before the start of treatment (results immediately before treatment including the first day of treatment), Week 78 (1.5 years later), Week 156 (3 years later) (or at discontinuation of treatment with this drug)

Walking ability rating scale
0: Good
1: Able to walk without difficulty despite of sensory disorder in the lower extremities
2: Able to walk without assistance despite of some difficulties
3a: Able to walk with one stick or crutch
3b: Able to walk with two sticks or crutches
4: Unable to walk, restricted to wheelchair or bedridden

7.3.2.8.8. Neurological assessment

Enter the test results for the following neurological assessments (1) to (6). The observation period is defined as follows and, if the observation period is discontinued, enter the test results at the time of discontinuation as much as possible.

[Timing of assessment] Before the start of treatment (results immediately before treatment including the first day of treatment), Week 52 (1 year later), Week 104 (2 years later), Week 156 (3 years later) (or at discontinuation of treatment with this drug)

(1) Motor

The motor will be assessed using a Medical Research Council (MRC) Scale.

)	No contraction
1	Flicker contraction
2	Muscle contraction with active motion with gravity eliminated
3	Full range of motion against gravity
4	Full range of motion against gravity with some resistance
5	Full range of motion against gravity with maximum resistance for that muscle

(2) Reflexes

Reflexes will be assessed with the following items: Present, Absent

(3) Light Touch

- (4) Pin Prick
- (5) Vibration
- (6) Position Sense

Light touch, pin prick, vibration, and position sense will be assessed with the following scales: Normal, Decrease, and Absent

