7.2.4. Observation period

3 years from the first day of treatment with this drug (156 weeks) However, the observation period for patients who started to receive this drug after May 2018 will be 1.5 years (78 weeks).

> Pfizer Confidential Page 12 of 37

If the treatment with this drug is discontinued during the observation period, the observation period will be until the day of discontinuation. If the dose of this drug is changed for the treatment of ATTR-CM, the observation period will be up to the date of last dose of 20 mg.

This study will be conducted using booklet type CRF.

The safety and efficacy assessments will be performed at the first visit (including the end date of the observation period) on or after the end date of the observation period (day of discontinuation if the treatment is discontinued during the observation period or date of the last dose of 20 mg if the dose was changed for the treatment of ATTR-CM). However, if a subject is lost to follow-up halfway through, the safety and efficacy assessments will be performed using the information on the last visit date.

Booklet No.	Observation period	
Booklet 1	First day of treatment to Week 78 (1.5 years)	
Booklet 2	Week 79 to Week 156 (3 years)	

7.3. Registration items and study items This study will be conducted according to the following schedule of observation.

Table 1. Schedule of observation

			Booklet 1		Book	det 2
Item	Registr ation form	At start of the study	Week 52 (1 year)	Week 78 (1.5 years)	Week 104 (2 years)	Week 156 (3 years)
Information to identify the subject			-	-	-	-
First day of treatment with this drug			-	-	-	-
Presence or absence of having received/used this drug at other sites, and if Yes, patient's duration of treatment	•					
THAOS registration status/THAOS registration ID						
State of concurrent medical examination	-					→
Background variables	-		-	-	-	-
History of previous treatment drugs for the targeted disease	-	•	-	-	-	-
Targeted drug use record	-	•				>
Concomitant therapy (drug therapy/ non-drug therapy)	-	•				
General tests (height, body weight, pulse, blood pressure)	-	•				
Clinical laboratory tests	-	•				→
Plasma concentration of tafamidis (to be performed only for patients with severe hepatic impairment)	-					•
Cardiovascular evaluation (ECG, echocardiography)	-					
Assessment of neurological function (NIS)	-		-		-	
Quality of Life (QOL-DN)	-		-		-	
Ambulatory state	-		-		-	

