Neurological assessment (motor function, tendon reflex, tactile sense, pain sensation, vibration sense, positional sense)	-	•	•	-	•	•
Medical assessment of physical symptoms	-	←		-		
Pregnancy	-	•				→
Record of study discontinuation	-					► ►
Confirmation of description concerning adverse events corresponding to major investigation item	-					→
Adverse events and tests for adverse events	-	◀				── →
Confirmation of survival						

Pfizer Confidential Page 14 of 37

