7.3.2.11. Effectiveness evaluation

The following 10 items should be evaluated for effectiveness:

(1) NIS (See Section 7.3.2.8.5.)

Evaluate the NIS total score, the NIS Upper Limb (NIS-UL) total score, the NIS Lower Limb (NIS-LL) total score, scores of cranial nervous system (sum of items 1 to 5), muscle weakness (sum of items 6 to 24), tendon reflex (sum of items 25 to 29), and sensation (index finger: sum of items 30 to 33, great toe: sum of items 34 to 37).

(2) Norfolk QOL-DN (See Section 7.3.2.8.6.)

Evaluate the TQOL scores (sum of all 35 items) and 5 domain scores (physical function/large nerve fiber disorder score, activities of daily living score, symptom score, small nerve fiber disorder score, and autonomic neuropathy score).

(3) Modified Body Mass Index (mBMI)

mBMI is calculated by multiplying BMI by serum albumin level.

(4) Ambulatory status (ambulatory ability scale in polyneuropathy dysfunction score)

Evaluate the ambulatory status (see Section 7.3.2.8.7 for details).

(5) Motor

Evaluate the motor function with MRC (16 items in total) (see Section 7.3.2.8.8 for details) scale. (6) Reflexes

Evaluate the tendon reflexes (5 items in total) (see Section 7.3.2.8.8 for details).

(7) Light Touch

Evaluate the tactile (11 items in total) (see Section 7.3.2.8.8 for details).

(8) Pin Prick

Evaluate the pain sensation (11 items in total) (see Section 7.3.2.8.8 for details). (9) Vibration

Evaluate the vibration sense (6 items in total) (see Section 7.3.2.8.8 for details). (10) Position Sense

Evaluate the positional sense (4 items in total) (see Section 7.3.2.8.8 for details).

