## 10. Appendices

## 10.1. Appendix 1: Details of Data Extraction

If there are multiple records within the acceptable window, the record closer to the target visit will be adopted.

## A1.1 Definition of Visit Timing 1

Endpoint	Visit (target)	Definition [acceptable window]
NIS	Before the start of treatment	[Before the start of treatment
QOL-DN	(BL; Base line)	with this drug, Week 4]
Ambulatory status	Week 78	[Weeks 4, Week 104]
Medical assessment of	Week 156	(> Week 104, ∞]
physical symptoms		

## A1.2 Definition of Visit Timing 2

Endpoint	Visit (target)	Definition [acceptable window]
mBMI	Before the start of	[Before the start of treatment
	treatment (BL)	with this drug, Week 4]
	Week 26	[Week 4, Week 39]
	Week 52	[Week 40, Week 65]
	Week 78	[Week 66, Week 91]
	Week 104	[Week 92, Week 117]
	Week 130	[Week 118, Week 143]
	Week 156	[Week 144, Week 169]

## A1.3 Definition of Visit Timing 3

Endpoint	Visit (target)	Definition [acceptable window]	
Neurological assessment	Before the start of treatment (BL)	[Before the start of treatment with this drug, Week 4]	
	Week 52	[Week 4, Week 78]	
	Week 104	[Week 79, Week 130]	
	Week 156	[Week 131, Week 182]	

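### For patients observed for 78 weeks, the neurological schedule and SAP A1.3 have no end-of-observation time point, so a value recorded then can be dropped from the summary or given the wrong week

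*Protocol*

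**What the plan says.** Protocol 7.2.4 sets a three-year observation period with one exception: "the observation period for patients who started to receive this drug after May 2018 will be 1.5 years (78 weeks"). The same section also says when the closing checks take place, for safety and for efficacy alike: "assessments will be performed at the first visit (including the end date of the observation period) on or after the end date". For the exception group this means Week 78 or later.

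Protocol 7.3.2.11 lists ten effectiveness items ("The following 10 items should be evaluated for effectiveness"). Items 5 to 10 come from the neurological assessment: motor, reflexes, light touch, pin prick, vibration and position sense. Protocol 7.3.2.8.8 times that assessment before treatment and then at "Week 52 (1 year later), Week 104 (2 years later), Week 156 (3 years later) (or at discontinuation of treatment with this drug"). Table 1 agrees and shows a dash at Week 78. By contrast, NIS, QOL-DN and ambulatory status (7.3.2.8.5 to 7.3.2.8.7) all have a Week 78 assessment.

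SAP 6.2 repeats the neurological schedule and adds the end or discontinuation of treatment. SAP 8.2.4.5 summarises the total, motor, reflex and sensation scores at the time points of A1.3. These are Week 52 (window Weeks 4 to 78), Week 104 (window "Week 79, Week 130") and Week 156 (window Weeks 131 to 182). If several records fall in one window, the one closest to the target week is kept.

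**The concern.** A patient on the short schedule who is still taking the drug at Week 78 has neither discontinued nor ended treatment. The item schedule therefore gives this patient one on-treatment neurological time point, Week 52. The general rule in 7.2.4, read on its own, asks for another at Week 78 or soon after. Sites could reasonably follow either.

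If a site does record a value at that visit, A1.3 has no row for it, and the calendar week alone decides its label. The Week 104 window runs from 25 weeks before its target to 26 weeks after. Patients on the 156-week schedule can fall on either side of 104, but a prompt end visit on the 78-week schedule always falls at the early edge. In a progressive disease, such values would make the Week 104 change from baseline look too small.

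The short schedule is provided for elsewhere: survival is confirmed at 1.5 years (protocol 7.3.2.13, SAP 6.2), and SAP 8.2.1 counts patients by planned observation of 78 or 156 weeks. The documents give no reason for leaving it out here.

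**Working it through.** **1. The plan's own figure.** 1.5 years × 52 = 78 weeks and 3 × 52 = 156 weeks, as stated in 7.2.4.

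**2. Applying A1.3 to an end-of-observation value.** The inputs are the three windows and the closest-to-target rule in SAP 10.1.

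| Week of end visit | Other record in the Week 52 window | Result in the 8.2.4.5 summary |
|---|---|---|
| 78 | one at Week 50, 52 or 60 | not used |
| 78 | none | labelled Week 52 |
| 79 to 130 | any | labelled Week 104 |
| 131 to 182 | any | labelled Week 156 |

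A Week 78 value lies 78 − 52 = 26 weeks from its target. It therefore also becomes the Week 52 value if the only other record in that window is before Week 26. If time is counted in fractions of a week, a value between Week 78 and Week 79 falls in no window.

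**3. One visit, two labels.** Take an end visit at Week 80.
- NIS, QOL-DN and ambulatory status (A1.1, window Weeks 4 to 104): Week 78.
- mBMI (A1.2, window Weeks 66 to 91): Week 78.
- Neurological assessment (A1.3): Week 104, which is 104 − 80 = 24 weeks ahead of the actual date.

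**4. Illustrative size.** The documents do not give the size of the short-schedule group. Its starts cover June 2018 to November 2019, which is 18 of the 73 calendar months of registration, but that is a share of time and not of patients. The assumptions are:
- change from baseline is linear in time, with the same slope in both groups;
- end visits fall at Weeks 79 to 90;
- all other values in the row are at Week 104;
- the group makes up 10%, 20% or 40% of the row.

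Shortfall of one mislabelled value = (104 − w)/104:
- w = 90: 14/104 = 13.5%
- w = 79: 25/104 = 24.0%

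Understatement of the row mean = share × shortfall:
- 10%: 1.3% to 2.4%
- 20%: 2.7% to 4.8%
- 40%: 5.4% to 9.6%

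**5. What NIS already covers at Week 78.** Comparing SAP 10.2.1 with 10.2.3, the 16 motor items are the muscles of NIS items 9 to 24, and the five reflexes are those of NIS items 25 to 29. NIS items 30 to 37 test touch, pin prick, vibration and joint position at the index finger and great toe.

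**The case against.** The strongest reply is that nothing conflicts. Section 7.2.4 is a general rule on when end assessments are made, while 7.3.2.8.8 and Table 1 agree with each other on which items are due when. If the specific governs the general, no Week 78 neurological value is requested, and mislabelling arises only if a site supplies one unasked. That reading is possible, but no sentence in the protocol adopts it. Section 7.2.4 speaks of efficacy assessments without exception, and A1.3 still has to say what happens to a value that is recorded.

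A reader might infer that six of the ten effectiveness items are simply lost at the end of observation for this group. The documents do not support that. NIS is collected at Week 78 and covers the same muscles and reflexes, so what is missing is mainly further sensory sites and a different grading scale. The SAP also analyses the six items as one endpoint group, one of six efficacy endpoints in SAP 5.2. A value left out of the summary may still appear in the SAP section 9 listing.

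A reader might also infer that the value is always either discarded or called Week 104. It can also become Week 52 or Week 156. Nor does the SAP plan a Week 104 to Week 156 change that could be distorted; it plans measured values and changes from baseline.

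Finally, the analysis is descriptive, with no hypotheses or decision rules (SAP 4.1, 4.2), and the shares, the Week 90 limit and linear progression are all assumptions. These points stand and limit the weight of the finding.

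**Conclusion.** The gap is real and modest. For patients who started after May 2018, the neurological schedule and A1.3 lack the end-of-observation time point that 7.2.4 implies. A value recorded at that visit can be left out of the 8.2.4.5 summary or given a week that does not describe it, while most other efficacy measures from the same visit are labelled Week 78. That holds for NIS, QOL-DN and ambulatory status up to Week 104 and for mBMI up to Week 91.

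The consequence is confined to descriptive summaries of one efficacy endpoint group. The understatement of about 1% to 10% in the Week 104 mean change is an illustration under the assumptions shown, not an estimate for this study. It applies only if sites recorded values at the end visit. If they did not, the row is unaffected, and the group simply has no neurological value at the end of observation, with NIS covering much of the same ground.

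**What to change.** **Protocol.** Reconcile 7.2.4 with 7.3.2.8.8 and Table 1 by stating whether a neurological assessment is expected at the end of 78-week observation.

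**SAP A1.3.** For patients whose planned observation after data linkage is 78 weeks:
- Add a row for Week 78 / end of observation, for example Weeks 66 to 91 as in A1.2.
- End their Week 52 window at Week 65, so that the two rows do not overlap.
- Do not count their end-of-observation value in the Week 104 row. State where an end visit after Week 91 goes: the listing only, or a wider window chosen in advance.
- Keep genuine Week 104 and Week 156 values in linked patients. The first day of treatment is site-specific (protocol 7.3.1), but SAP 8.2.1 re-dates linked patients from their earliest start. A patient who began at a second site after May 2018 can therefore truly have reached those weeks.

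**Cost.** The A1.3 change is SAP wording and needs no new data. Somewhat fewer patients will be in the Week 104 row, and records at Weeks 66 to 78 in this group will no longer count as Week 52. Adding the assessment to the CRF is a larger matter. With every site bilateral except the trunk, it is 32 + 10 + 21 + 21 + 12 + 8 = 104 graded results per patient. It may also be too late, since data collection was planned to end in May 2021 and SAP version 10.0 is dated March 2023.
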